We will also examine **exploratory hypotheses**, such as whether there are baseline covariates which will help to significantly enhance the prediction of response to treatments, e.g., gender, race, treatment site (primary care vs. specialty clinic), social support, co-treatments. This will enhance the precision medicine implications of the study.

H2: serious adverse events, falls, and fall-related injuries are the safety outcomes. Cox models examining time to event (with Anderson & Gill⁶⁴ extensions for repeated events) will compare the treatment arms during both the acute phase and the continuation in terms of serious adverse events, falls, and fall-related injuries.

We will also compute rates of side effects in each arm, as specifically recommended by patient stakeholders. These data are not hypothesis-testing, but they support the patient-centered goal of allowing clinicians and patients to know what to expect in terms of side effects from treatment.

H3: Moderator analyses (Heterogeneity of Treatment Effects).

Confirmatory analysis (HT-1): Effectiveness and safety differences between treatment arms will be moderated by age. Specifically, with increasing age effectiveness differences between treatment arms will decrease, and safety differences between treatment arms will increase.

Rationale: Our stakeholders demand that we move past the current "one size fits all" paradigm of antidepressant prescribing. Precision treatment would greatly improve older adults' quality of life.

Data analysis plan for moderator testing: We will include the treatment by age group (<70 vs >70) by time interaction to the linear models described above to test for both the benefits and risks for the treatment alternatives.

We are well-powered for a confirmatory moderator analysis examining how age modulates the differences between treatment arms in comparative benefits and risks, because of our recruitment strategy aiming for equally-sized strata of ages (60-70 and >70). Age will be treated as a categorical variable, comparing relative benefits and risks of antidepressants in those aged <70 to those aged >70.

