Here are some scenarios of the types of treatment modulators by age that we will be able to detect with a power > 85% (using SAS's GLMPOWER): (1) If treatment arm A has superior effectiveness over arm B by 2.3 points more than what would be predicted based on age and treatment effects on Psychological Well-being for age 60-70 but no difference between arms for age >70; (2) If treatment arm A has a superior effectiveness over arm B in terms of 13% higher remission rate for age 60-70, but there is no difference between arms for age>70.

Exploratory moderator analyses based on aging-related brain and systemic health variables: Our next step will be to analyze three aging-related variables –impairment in executive cognitive function, frailty, and medical complexity – treated both as continuous variables and categorical variables, using the same models as with chronological age.

Finally, we will examine the relative strength of these moderator variables by performing a combined moderator test.^{76,77} This exploratory analysis incorporates all of the age-related variables into models of each effectiveness and safety finding from hypothesis-testing.

Notes regarding these Heterogeneity of Treatment Effect (moderator) analyses: We will perform statistical contrasts between treatment arms as a function of thee pre-specified moderator variables, and we will report all of these prespecified analyses, as well as post-hoc analyses, in published reports.

H2 Sample Size Determination and Power

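### The protocol's >85% power for age moderation of remission is not delivered under its own planning inputs: about 53-62% at 1,500 patients and 25-29% at the SAP's reduced size

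*Protocol*

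**What the plan says.** Protocol section H1, under the moderator hypothesis (HT-1), labels the age analysis confirmatory and predicts that "with increasing age effectiveness differences between treatment arms will decrease". The test is an interaction: "We will include the treatment by age group (<70 vs >70) by time interaction to the linear models described above". On size it says "We are well-powered for a confirmatory moderator analysis examining how age modulates the differences between treatment arms", and gives as the reason a "recruitment strategy aiming for equally-sized strata of ages (60-70 and >70").

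It then lists scenarios "that we will be able to detect with a power > 85" per cent, computed with SAS GLMPOWER. The second is a superiority of arm A over arm B in the form of a "13% higher remission rate for age 60-70, but there is no difference between arms for age>70". The first concerns psychological well-being, where A exceeds B "by 2.3 points more than what would be predicted based on age and treatment effects" at 60-70. The closing notes say "We will perform statistical contrasts between treatment arms" as a function of the moderators. No alpha, sidedness, base remission rate or third-arm rate is given for these scenarios.

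Protocol section H2 gives the general planning inputs: 500 per Step 1 arm and remission around 40%.

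The SAP differs in two ways. Sections 2.2.2 and 6.2 make the age analysis exploratory. Section 3.3 cuts the sample to 708, of whom 123 entered Step 2 directly. The SAP neither repeats nor withdraws the power figure.

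**The concern.** An interaction is estimated much less precisely than a treatment difference in the whole sample, because it compares two differences, each based on half the patients. A 13-point interaction at 250 per cell therefore looked unlikely to have more than 85% power.

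Whether age changes the relative benefit of the strategies is Aim 2 of the trial. A reader who trusts the stated power would expect a true 13-point interaction to be missed less than 15% of the time, and could take a non-significant result as evidence that the arms compare alike at all ages.

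**Working it through.** **Inputs.** 500 per arm (protocol H2); 1:1:1 allocation (protocol E, Treatment Group Assignment); equal age strata (protocol H1), hence 250 per arm-by-age cell; logit model for remission (protocol H1, H1b). Remission near 40% is an assumption taken from the H2 power table. Alpha is not stated for the moderator test, so three levels are shown. One-sided .05 is included because HT-1 states a direction, and .05/3 because the protocol uses it for the H1a pairwise contrasts.

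**Check of the inputs on the protocol's own table.** Two proportions, n = 500 per arm, two-sided .05/3 (z = 2.394):

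power = Φ{[d − z√(2p̄(1−p̄)/n)] / √([p₁(1−p₁)+p₂(1−p₂)]/n)}

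With rates at or around 40%, d = 10.2 points gives 0.80-0.84 and d = 11.5 points gives 0.90-0.93. The table states .8 and .9, so its remission row reproduces.

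**A-versus-B interaction.** SE = √(Σp(1−p)/250) over the four cells; power = Φ(0.13/SE − z), with z = 1.960, 1.645 or 2.394.

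Example, 53/40 at 60-70 and 40/40 at >70: Σp(1−p) = .2491 + 3(.24) = .9691; SE = √(.9691/250) = .0623; .13/.0623 = 2.09; power = Φ(2.09 − 1.96) = .55.

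| A/B at 60-70; A/B at >70 (%) | SE | two-sided .05 | one-sided .05 | .05/3 |
|---|---|---|---|---|
| 40/27; 27/27 | .0577 | .616 | .729 | .445 |
| 43/30; 30/30 | .0592 | .594 | .710 | .422 |
| 40/27; 40/40 | .0606 | .574 | .692 | .402 |
| 48/35; 35/35 | .0611 | .567 | .686 | .396 |
| 46.5/33.5; 40/40 | .0617 | .559 | .678 | .387 |
| 53/40; 40/40 | .0623 | .551 | .671 | .380 |
| 58/45; 45/45 | .0628 | .544 | .665 | .373 |

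On the planned logit scale the same cells give .534-.603, .655-.718 and .364-.432. Across both scales: **53-62%, 65-73% and 36-45%**.

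**Other forms of the test, at .05.**
- Three-arm 2-df interaction: 43-65% if the third arm's rate at 60-70 lies between those of A and B. It reaches 85% only if that rate is about 5-8 points below B or above A.
- A against the average of the other two arms, third arm equal to B: 67-73% two-sided, 77-83% one-sided.
- A against B inside the 60-70 stratum only, 250 v 250, two-sided: 83-87%. This does not test moderation.

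**What 85% would need** (pairwise, two-sided .05). Patients per cell = (1.960 + 1.036)² × Σp(1−p)/.13² = 442-524, or about 2,650-3,140 over six cells. At 250 per cell, the detectable interaction is 2.996 × SE = 17-19 points.

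**Reduced sample** (SAP 3.3). 708 − 123 = 585 in Step 1; 585/6 ≈ 97 per cell if the arms and age strata stay equal. Example with the 53/40; 40/40 cells: SE = √(.9691/97) = .100; power = Φ(1.30 − 1.96) = .255. Over all cells and both scales: **25-29%**. The expected 95% CI half-width, 1.96 × SE, is 18-20 points, against 11-12 points at 250 per cell.

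**Well-being scenario.** SD of change = 8 (sd 8, r = .5); SE = 8√(4/250) = 1.012. A 2.3-point interaction has 62% power; a 4.6-point one has over 99%.

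**The case against.** The strongest objection is that the figure is not reproducible, which is weaker than wrong. A 2×3 model needs six cell rates, and the protocol describes only two arms. The treatment-by-age term has 2 df with three arms, so a pairwise test is one reading among several. Some inputs do reach 85%. For example, A/B/third arm of 53/40/32 at 60-70 with 40% in all older cells gives .88, and 40/27/20 with 27% in the older cells gives .90. Rates of 23 v 10, with 10 in both older cells, give .87 on the risk-difference scale. This stands as far as the origin of the figure goes. But none of those inputs is in the protocol. The low-rate case is far from the 40% in H2 and gives only .71 on the planned logit scale.

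A related objection is that the remission scenario may share the looser sense of the well-being scenario and mean a larger interaction; 26 points would have about 99%. The remission wording does not carry the qualifying phrase, so 13 against 0 is the plain reading.

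Third, the SAP has already downgraded the analysis, plans confidence intervals (sections 3.4 and 4.1), and is the guiding document for the quantitative analyses (section 2.2.3). This limits the consequence. It does not withdraw the protocol's label or figure.

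Finally, nothing in either document plans to read a null interaction as equality. The misreading is a risk for readers, not a stated intention.

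**Conclusion.** The stated power of more than 85% is not delivered under the protocol's own planning inputs. At 250 per cell and remission near 40%, a true 13-point A-versus-B interaction would be missed about 38-47% of the time at two-sided .05. At the SAP's sample it would be missed about 71-75% of the time. One-sided testing, .05/3, and the 2-df test with the third arm between A and B all stay below 85%.

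The result rests on the 40% base rate, equal age strata, equal arms and no dropout. The 8% dropout per step in the protocol's milestone schedule would lower power slightly, to about 52% at 1,500 patients with rates centred on 40%.

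Two stronger readings are tempting and not supported. A reader might infer that the figure came from a subgroup comparison within ages 60-70, since that gives 83-87%. The protocol does not show its calculation, so this cannot be established. A reader might also infer that the 2.3-point well-being scenario is wrong. It is only ambiguous.

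The point concerns the stated figure and the interpretation of a null age interaction, not the validity of the test or the design.

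**What to change.** In the moderator part of protocol H1:

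- Delete the power figure for the remission scenario. Alternatively, replace it with the interaction power for both samples: 53-62% at 1,500 and 25-29% at the current size (pairwise, two-sided .05, remission near 40%). Giving only the first would leave another overstated figure.
- State alpha, sidedness, base rate, cell size, and whether the test is pairwise or 2-df; if 2-df, also the third arm's rate.
- State which interaction the 2.3-point well-being scenario means.
- Drop the description of the age analysis as well powered and confirmatory, and label HT-1 exploratory, to match SAP 2.2.2 and 6.2.

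In reporting, give the age interaction with its 95% confidence interval, and say that a non-significant result is not evidence of equal effects across ages.

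The cost is wording and a less favourable stated figure. The test, design and enrolment do not change.

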⁷ Increase in proportion experiencing a fall, around a 20% baseline rate

⁸ Increase in proportion experiencing an injurious fall, around a 4% baseline rate

⁹ Scale point change, sd=9

11 Confidentiality and Security

Participant confidentiality and data security will be facilitated with the following tools and processes:

The primary data collection and management tool for this study will be REDCap (Research Electronic Data Capture) databases created and maintained by the Data Management team at the Coordinating Site.

REDCap's features support best practices for data confidentiality and security. REDCap (Research Electronic Data Capture) is a secure, web-based application designed to support data capture for research studies, providing: • user authentication and role-based security • collaborative access to data across academic departments and institutions • intuitive electronic case report forms (CRFs) • real-time data validation, integrity checks and other mechanisms for ensuring data quality (e.g. double-data entry options) • data attribution and audit capabilities • protocol document storage and sharing • central data storage and backups • data export functions for common statistical packages • data import functions to facilitate bulk import of data from other systems. Data that is imported and/or exported will be kept on a secure department network.

Secure data collection in sites with inconsistent internet connections will be facilitated by using the REDCap Mobile App on password-protected tablet devices. The REDCap Mobile App allows for secure data transmission (using SSL/HTTPS), secure data storage, secure user authentication, and remote lockout capability. Details of the security features for the REDCap Mobile App can be located here: https://projectredcap.org/security.pdf

Washington University Security Architecture: To ensure patient privacy and compliance with HIPAA regulations, data is stored behind the university approved, hardware firewalled network. Access is context specific to each user and individual collection protocols such that it supports both the regulatory guidelines (e.g. HIPAA and patient privacy) and proprietary (intellectual property) concerns.

Hard copy records will be stored in a locked drawer/cabinet in a locked office/suite. The study team will treat all subject/patient data used and disclosed in connection with this study in accordance with all applicable privacy laws, rules and regulations, including all applicable provisions of HIPAA and its implementing regulations. Study records sent to the sponsor will not include participant's name to protect patient confidentiality.

12 Training

The Coordinating Site will ensure that the PI and Study Coordinator at each site have access to appropriate training materials in study procedures, assessments, and recordkeeping. The PI and/or Study Coordinator at each site are responsible for ensuring and documenting that all research team members at their respective sites are trained and supervised appropriately prior to conducting any study procedures.

Training of each treating physician will be the responsibility of each site working with the treating physician's patient and will be done according to the training plan outlined in the manual of procedures.

13 Case Report Forms and Source Documents

This study will utilize REDCap-based electronic Case Report Forms (e-CRF's) for data capture and storage. Source documents, including laboratory values, medical records and physician communications will be maintained at each site to verify adherence to protocol, inclusion/exclusion criteria, and data accuracy.

14 Records Retention

The investigator will maintain records in accordance with state and federal government regulations standards of Good Clinical Practice, and applicable institutional research policies and procedures. All electronic and hard copy research records and imaging data are stored for at least seven years beyond the close of the study.

J Study Monitoring, Auditing, and Inspecting

J1 Study Monitoring Plan

In order to fulfill our ethical, legal, and scientific obligations to conducting this study in a detailed and orderly manner, the Coordinating site may visit the other participating sites during the study, as well as communicate frequently via telephone and written communications.

J2 Auditing and Inspecting

The Coordinating site may conduct study site audits. Audits would typically include, but are not be limited to, presence of required documents, the informed consent process, and review of research records. Most auditing will be done remotely via review of REDCap records.

Regulatory authorities may inspect the investigator during or after the study. The investigator will cooperate with such inspections and will contact the Coordinating site immediately if such an inspection occurs.

K Study Administration

K1 Organization and Participating Centers

This is a collaborative, multi-site study with five academic sites: Washington University (Coordinating Site), University of Pittsburgh, University of Toronto, University of California Los Angeles, and Columbia University.

Ongoing communication and coordination between sites will be facilitated by regular conference calls attended by PI's and appropriate personnel. Records of these conference calls will be maintained by the Coordinating Site.

A Manual of Procedures will be provided to sites and updated as needed to ensure consistent conduct of the trial across sites.

K2 Funding Source

This project is funded by the Patient Centered Outcomes Research Institute (PCORI).

K3 Participant Compensation

Compensation plans for participants will be determined by each study site and approved by their respective IRB's. Compensation plans must adhere to the following guidelines:

- All participants should receive equal compensation for equivalent time and effort..
- The compensation amount should be reasonable for the time and effort of the participant.
- Compensation may not be held until completion of all study activities. If there are multiple visits or study procedures compensation must be pro-rated for the completion of each visit or part of the study.
- Information about compensation must be included in the Consent Document.

K4 Milestone Schedule

The overall timetable for the study will follow the milestone schedule agreed upon in the PCORI contract. Any barriers or delays to completing milestones per the schedule should be discussed with the Coordinating Site, who will bring significant issues to the attention of the PCRI program officer as needed.

	Milestone Name	Description	Projected Completion Date
Α	Effective Date		10/1/2016
B1	IRB Approval Obtained	Obtain local IRB approval	1/1/2017
B2	Formation of Stakeholder Advisory Board (SAB)	Finalize the composition of the SAB to include members recommended by PCORI. Document the members of the SAB including the organization, title, and stakeholder group they represent. Deliverable: Complete SAB roster (including the organization, title, and stakeholder group they represent).	1/1/2017
В3	In-person Kickoff Meeting. Initiate implementation and start recruitment	Study startup meeting. Launch study and begin recruitment in some practices once approved by DSMB. Kickoff meeting to include investigators, research coordinators, and other key partners. Train staff and clinicians from each site on the study protocol.	1/12/17- 1/13/17
В4	Stakeholder Advisory Board Kickoff Meeting	Kick off meeting for the Stakeholder Advisory Board. Deliverable: Meeting minutes and/or summary of the meeting discussion should document the input of the patient/stakeholder members and should be submitted with the Interim Progress Report	1/12/17- 1/13/17
B5	Protocol Complete	Complete the final study protocol and submit to [contact] and cc the Program Officer and Associate	2/1/2017
В6	Finalize study	Finalize assessments, materials, study protocol, and statistical analysis plan in collaboration with SAB. Submit materials as attachment in next Interim Progress Report. Design database and implement data entry process.	2/1/2017

Select and register project at appropriate stay design (Clinicaltrals gov, RoPR, or other as approved by PCDRI before study start date) B8 IRB approval Approval Approval by all sites' IRBs Minutes from 1st DSMB meeting. Review and discuss subject data collected to date. In the interim progress report, include any significant data & safety monitoring issues that occurred in the reporting period. If there are any serious unanticipated problems (e.g., serious adverse event, serious safety issue, or other serious problem) reliating to the research study, awardee institutions must notity PCORI promptity, but no later than 10 days after. C1 Complete implementation C2 Stakeholder Advisory Board Meeting. Deliverables: Meeting minutes and/or summary of the meeting discussion should document the input of the patient/stakeholder members and should be submitted with the Interim Progress Report. Report grother grother in period. If there are any serious unanticipated problems (e.g., serious adverse event, serious safety issue, or other serious problem) reliable to the research study, awardee institutions must notity PCORI promptity, but no later than 10 days after. C3 Stakeholder Advisory Board Meeting, Deliverables: Meeting minutes and/or summary of the meeting discussion should document the input of the patient/stakeholder members and should be submitted with the Interim Progress Report and stoud be submitted with the Interim Progress Report and stoud and safety monitoring Issues that occurred in the reporting period. If there are any serious unanticipated problems (e.g., serious adverse event, serious safety issue, or other serious problem) reliance to the serious problem? (e.g., serious adverse event, serious safety issue, or other serious problem) reliance to the serious problem? (e.g., serious adverse event, serious safety issue, or other serious problem) reliance to the reservoir of the recruitment progress report, include any significant data & safety monitoring Issues that occurred in the reporting period. If t	_			_
DSMB meeting Propose DSMB meeting Propose Propose DSMB meeting Propose Propose DSMB meeting Propose DSMB meet	В7	at appropriate site for the study design (Clinicaltrials.gov, RoPR, or other as approved by PCORI before study start		3/1/2017
DSMB meeting Propose DSMB meeting Propose Propose DSMB meeting Propose Propose DSMB meeting Propose DSMB meet	В8	IRB approval	Approval by all sites' IRBs	4/1/2017
C1 Complete implementation C2 Complete implementation C3 Stakeholder Advisory Board Meeting C3 DSMB meeting C6 Report Submission C6 Report Submission C7 DSMB meeting C8 DSMB meeting C9 DSMB meeting C9 DSMB meeting C9 DSMB meeting C9 Stakeholder Advisory C9 DSMB meeting C9 DSMB meet	В9	DSMB meeting	collected to date. In the interim progress report, include any significant data & safety monitoring issues that occurred in the reporting period. If there are any serious unanticipated problems (e.g., serious adverse event, serious safety issue, or other serious problem) relating to the research study, awardee institutions must	
C2 Complete implementation randomize 125 participants each quarter for 12 quarters (total randomized N=1,500; approximately 42 participants recruited per month). 7/1/2017	В	Report Submission	Submit Progress Report, Using Interim Progress Report Template	4/1/2017
Stakeholder Advisory Board Meeting and/or summary of the meeting discussion should document the input of the patient/stakeholder members and should be submitted with the Interim Progress Report Minutes from 2nd DSMB meeting. Review and discuss subject data collected to date. In the interim progress report, include any significant data & safety monitoring issues that occurred in the reporting period. If there are any serious unanticipated problems (e.g., serious adverse event, serious safety issue, or other serious problem) relating to the research study, awardee institutions must notify PCORI promptly, but no later than 10 days after. Complete 25% of recruitment Complete 25% of recruit 375 participants in total (approximately 42 participants recruited per month). Document and send to PCORI Program Officer and Associate. Minutes from 3rd DSMB meeting. Review and discuss subject data collected to date. In the interim progress report, include any significant data & safety monitoring issues that occurred in the reporting period. If there are any serious unanticipated problems (e.g., serious adverse event, serious safety issue, or other serious problem) relating to the research study, awardee institutions must notify PCORI promptly, but no later than 10 days after. Stakeholder Advisory Board Meeting. Deliverables: Meeting minutes and/or summary of the meeting discussion should document the input of the patient/stakeholder members and should be submitted with the Interim Progress Report. Using Interim Progress Report Template Start follow-up data collection Start follow-up data collection Complete 50% of recruit 750 participants in total (approximately 42 participants recruited per month). Document and send to PCORI Program Officer	C1	Complete implementation	randomize 125 participants each quarter for 12 quarters (total randomized N=1,500; approximately 42 participants recruited per	7/1/2017
C3 DSMB meeting cignor of the complete state of the progress Report. Using Interim Progress Report Template 10/1/2017 C Report Submission Submit Progress Report, Using Interim Progress Report Template 10/1/2017 C Complete 25% of recruitment Recruit 375 participants in total (approximately 42 participants recruited per month). Document and send to PCORI Program Officer and Associate. Minutes from 3rd DSMB meeting. Review and discuss subject data collected to date. In the interim progress report, include any significant data & safety monitoring issues that occurred in the reporting period. If there are any serious unanticipated problems (e.g., serious adverse event, serious safety issue, or other serious problem) relating to the research study, awardee institutions must notify PCORI promptly, but no later than 10 days after. D3 Stakeholder Advisory Board Meeting Deliverables: Meeting minutes and/or summary of the meeting discussion should be submitted with the Interim Progress Report D4 Report Submission Submit Progress Report, Using Interim Progress Report Template E1 Start follow-up data collection Submit Progress Report, Using Interim Progress Report Template Complete 50% of recruitment continuation phase (based on 45% remission rate and 8% attrition in each of steps 1 and 2). Recruit 750 participants in total (approximately 42 participants recruited per month). Document and send to PCORI Program Officer recruitment recruited per month). Document and send to PCORI Program Officer	C2		and/or summary of the meeting discussion should document the input of the patient/stakeholder members and should be submitted	7/1/2017
Complete 25% of recruitment Recruit 375 participants in total (approximately 42 participants recruitment in the interim progress Report Template Complete 25% of recruitment Recruit 375 participants in total (approximately 42 participants recruitment in the interim Progress Report Template Complete 50% of recruitment Complete 50% of recruitment Complete 50% of recruitment Recruit 750 participants in total (approximately 42 participants recruitment and send to PCORI Program Officer Complete 50% of recruitment Complete 50% of	С3	DSMB meeting	collected to date. In the interim progress report, include any significant data & safety monitoring issues that occurred in the reporting period. If there are any serious unanticipated problems (e.g., serious adverse event, serious safety issue, or other serious problem) relating to the research study, awardee institutions must	10/1/2017
D1 Complete 25% of recruitment Recruit 375 participants in total (approximately 42 participants recruited per month). Document and send to PCORI Program Officer and Associate. Minutes from 3rd DSMB meeting. Review and discuss subject data collected to date. In the interim progress report, include any significant data & safety monitoring issues that occurred in the reporting period. If there are any serious unanticipated problems (e.g., serious adverse event, serious safety issue, or other serious problem) relating to the research study, awardee institutions must notify PCORI promptly, but no later than 10 days after. Stakeholder Advisory Board Meeting. Deliverables: Meeting minutes and/or summary of the meeting discussion should document the input of the patient/stakeholder members and should be submitted with the Interim Progress Report Start follow-up data collection Submit Progress Report, Using Interim Progress Report Template 4/1/2018	С	Report Submission		
DSMB meeting collected to date. In the interim progress report, include any significant data & safety monitoring issues that occurred in the reporting period. If there are any serious unanticipated problems (e.g., serious adverse event, serious safety issue, or other serious problem) relating to the research study, awardee institutions must notify PCORI promptly, but no later than 10 days after. Stakeholder Advisory Board Meeting. Deliverables: Meeting minutes and/or summary of the meeting discussion should document the input of the patient/stakeholder members and should be submitted with the Interim Progress Report D Report Submission Submit Progress Report, Using Interim Progress Report Template 250 participants finish 4-month acute phase and begin 12-month continuation phase (based on 45% remission rate and 8% attrition in each of steps 1 and 2). Complete 50% of recruitment Recruit 750 participants in total (approximately 42 participants recruited per month). Document and send to PCORI Program Officer	D1	•	recruited per month). Document and send to PCORI Program Officer	
Stakeholder Advisory Board Meeting Deliverables: Meeting minutes and/or summary of the meeting discussion should document the input of the patient/stakeholder members and should be submitted with the Interim Progress Report 4/1/2018 Start follow-up data collection Start follow-up data continuation phase (based on 45% remission rate and 8% attrition in each of steps 1 and 2). Recruit 750 participants in total (approximately 42 participants recruited per month). Document and send to PCORI Program Officer	D2	DSMB meeting	collected to date. In the interim progress report, include any significant data & safety monitoring issues that occurred in the reporting period. If there are any serious unanticipated problems (e.g., serious adverse event, serious safety issue, or other serious problem) relating to the research study, awardee institutions must	4/1/2018
Start follow-up data collection 250 participants finish 4-month acute phase and begin 12-month continuation phase (based on 45% remission rate and 8% attrition in each of steps 1 and 2). Complete 50% of recruitment 7/1/2018 Recruit 750 participants in total (approximately 42 participants recruited per month). Document and send to PCORI Program Officer	D3	-	Stakeholder Advisory Board Meeting. Deliverables: Meeting minutes and/or summary of the meeting discussion should document the input of the patient/stakeholder members and should be submitted	
E1 Start follow-up data collection	D	Report Submission	Submit Progress Report, Using Interim Progress Report Template	4/1/2018
E2 Complete 50% of recruitment recruitme	E1		continuation phase (based on 45% remission rate and 8% attrition in	
	E2		recruited per month). Document and send to PCORI Program Officer	10/1/2018

. –			_
E3	Stakeholder Advisory Board Meeting	Stakeholder Advisory Board Meeting. Deliverables: Meeting minutes and/or summary of the meeting discussion should document the input of the patient/stakeholder members and should be submitted	
		with the Interim Progress Report	10/1/2018
E4	Begin semi-structured		
	interviews	Begin semi-structured interviews (goal N=150)	10/1/2018
E5	DSMB meeting	Minutes from 4th DSMB meeting. Review and discuss subject data collected to date. In the interim progress report, include any significant data & safety monitoring issues that occurred in the reporting period. If there are any serious unanticipated problems (e.g., serious adverse event, serious safety issue, or other serious problem) relating to the research study, awardee institutions must notify PCORI promptly, but no later than 10 days after.	10/1/2018
Е	Report Submission	Submit Progress Report, Using Interim Progress Report Template	
	Report Submission		10/1/2018
F1	DSMB meeting	Minutes from 5th DSMB meeting. Review and discuss subject data collected to date. In the interim progress report, include any significant data & safety monitoring issues that occurred in the reporting period. If there are any serious unanticipated problems (e.g., serious adverse event, serious safety issue, or other serious problem) relating to the research study, awardee institutions must notify PCORI promptly, but no later than 10 days after.	4/1/2019
		Stakeholder Advisory Board Meeting. Deliverables: Meeting minutes	
F2	Stakeholder Advisory	and/or summary of the meeting discussion should document the	
12	Board Meeting	input of the patient/stakeholder members and should be submitted	4/4/2040
F	Devent Culturiesies	with the Interim Progress Report	4/1/2019
	Report Submission	Submit Progress Report, Using Interim Progress Report Template	4/1/2019
G1	Complete 25% of follow- up data collection	225 participants finish 4-month acute phase and begin 12-month continuation phase (estimate of 12-month completers = 225, based on 45% of participants remitting at each of steps 1 and 2, 8% of participants dropping out during each of steps 1 and 2, and additional 10% dropping out during the 1-year continuation phase). The Interim Progress Report should include summary of data collected to date for review of patient accrual, patient characteristics and data quality.	7/1/2019
		Recruit 1125 participants in total (approximately 42 participants	7/1/2013
G2	Complete 75% of	recruited per month). Document and send to PCORI Program Officer	
	recruitment	and Associate.	7/1/2019
G3	Complete semi-structured interviews	Complete semi-structured interviews (goal N=150)	7/1/2019
G4	DSMB meeting	Minutes from 6th DSMB meeting. Review and discuss subject data collected to date. In the interim progress report, include any significant data & safety monitoring issues that occurred in the reporting period. If there are any serious unanticipated problems (e.g., serious adverse event, serious safety issue, or other serious problem) relating to the research study, awardee institutions must notify PCORI promptly, but no later than 10 days after.	10/1/2019
G5	Stakeholder Advisory Board Meeting	Stakeholder Advisory Board Meeting. During this meeting, findings from semi-structured interviews analyzed and provided to SAB. Deliverables: Meeting minutes and/or summary of the meeting discussion should document the input of the patient/stakeholder members and should be submitted with the Interim Progress Report	10/1/2019
G	Report Submission	Submit Progress Report, Using Interim Progress Report Template	10/1/2019
H1	Complete recruitment	Recruit 1500 participants total (approximately 42 participants recruited per month). Document and send to PCORI Program Officer and Associate.	
		מווע השטטומנב.	1/1/2020

		·	_
H2	Complete 50% of follow- up data collection	450 participants finish 4-month acute phase and 12-month continuation phase (estimate of 12-month completers = 450, based on 45% of participants remitting at each of steps 1 and 2, 8% of participants dropping out during each of steps 1 and 2, and additional 10% dropping out during the 1-year continuation phase). The Interim Progress Report should include summary of data collected to date for review of patient accrual, patient characteristics and data quality.	4/1/2020
НЗ	DSMB meeting	Minutes from 7th DSMB meeting. Review and discuss subject data collected to date. In the interim progress report, include any significant data & safety monitoring issues that occurred in the reporting period. If there are any serious unanticipated problems (e.g., serious adverse event, serious safety issue, or other serious problem) relating to the research study, awardee institutions must notify PCORI promptly, but no later than 10 days after.	4/1/2020
H4	Stakeholder Advisory Board Meeting	Stakeholder Advisory Board Meeting. Deliverables: Meeting minutes and/or summary of the meeting discussion should document the input of the patient/stakeholder members and should be submitted with the Interim Progress Report	4/1/2020
Н	Report Submission	Submit Progress Report, Using Interim Progress Report Template	4/1/2020
l1	Complete acute phase	All participants finish 4-month acute phase	10/1/2020
12	DSMB meeting	Minutes from 8th DSMB meeting. Review and discuss subject data collected to date. In the interim progress report, include any significant data & safety monitoring issues that occurred in the reporting period. If there are any serious unanticipated problems (e.g., serious adverse event, serious safety issue, or other serious problem) relating to the research study, awardee institutions must notify PCORI promptly, but no later than 10 days after.	10/1/2020
13	Stakeholder Advisory Board Meeting	Stakeholder Advisory Board Meeting. Deliverables: Meeting minutes and/or summary of the meeting discussion should document the input of the patient/stakeholder members and should be submitted with the Interim Progress Report	10/1/2020
ı	Report Submission	Submit Progress Report, Using Interim Progress Report Template	10/1/2020
